## 4. STATISTICAL ANALYSIS AND REPORTING

### 4.1. Introduction

Data processing, tabulation of descriptive statistics, calculation of inferential statistics, and graphical representations will primarily use SAS (release 9.4 or higher). If the use of other software is warranted, the final statistical methodology report will detail what software was used for what purposes.

Continuous (quantitative) variable summaries will include the number of subjects (n) with non-missing values, mean, standard deviation (SD), median, minimum, and maximum.

Categorical (qualitative) variable summaries will include the frequency and percentage of subjects who are in the particular category or each possible value. In general, the denominator for the percentage calculation will be based upon the total number of subjects in the study population for each treatment group, unless otherwise specified.

The minimum and maximum will be reported with the same degree of precision (i.e., the same number of decimal places) as the observed data. Measures of location (mean and median) will be reported to 1 degree of precision more than the observed data and measures of spread (SD, standard error [SE]) will be reported to 2 degrees of precision more than the observed data.

Percentages will be presented to 1 decimal place, unless otherwise specified.

Unless otherwise indicated, all statistical tests will be conducted at the 0.1 significance level using 2-tailed tests, and *P* values will be reported. For the purposes of statistical comparisons, the vehicle BID and vehicle QD groups will be pooled together. Testing will be performed for:

- ARQ-252 cream 0.3% QD versus vehicle cream (all dose frequencies)
- ARQ-252 cream 0.3% BID versus vehicle cream (all dose frequencies)
- ARQ-252 cream 0.1% QD versus vehicle cream (all dose frequencies)
- ARQ-252 cream (all strengths and dose frequencies) versus vehicle cream (all dose frequencies)
- ARQ-252 cream 0.3% (all dose frequencies) versus vehicle cream (all dose frequencies)

Corresponding 90% and 95% confidence intervals (CIs) will be presented for statistical tests. Testing will be performed for the primary endpoint of IGA clear or almost clear, for change from baseline in the HECSI score, and for the percent change from baseline in the HECSI score; however, *P* values will be provided for informational purposes for other endpoints as specified in [Section 8](#). The primary statistical comparisons and evaluations of secondary endpoints will not be adjusted for multiplicity.

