##### Phase 2b (Cohort 2):

The primary endpoint of Cohort 2 is:

- The rate of an Investigator Global Assessment (IGA) score of “clear” or “almost clear” at Week 12

The primary estimand for the primary efficacy endpoint of this study is the odds of achieving IGA score of “clear” or “almost clear” (i.e., IGA success) at 12 weeks; that is, the ratio of the odds of achieving IGA success at 12 weeks ARQ-252 relative to the odds of success at 12 weeks of using a matching vehicle cream. In the course of the 12-week randomized treatment period, subjects may be exposed to possible known or unknown intercurrent events that could possibly affect the estimand, such as treatment discontinuation due to a specific adverse effect or perhaps a lack of effect. The “Treatment Policy Strategy” has been adopted for handling all known or unknown intercurrent events in this study. To this end, the ITT principle will serve as the analytical basis for interpreting the estimand. In other words, the odds ratio of achieving IGA success for ARQ-252 relative to vehicle at 12 weeks will be evaluated regardless of the occurrence of any such intercurrent event. This estimand shall be estimated using the Cochran-Mantel-Haenszel (CMH) approach and applies to the following treatment comparisons:

- ARQ-252 cream 0.3% BID versus vehicle cream (all dose frequencies)
- ARQ-252 cream 0.3% QD versus vehicle cream (all dose frequencies)
- ARQ-252 cream 0.1% QD versus vehicle cream (all dose frequencies)
- ARQ-252 cream (all strengths and dose frequencies) versus vehicle cream (all dose frequencies)
- ARQ-252 cream 0.3% (all dose frequencies) versus vehicle cream (all dose frequencies)

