### **3.2. Sample Size and Power**

Cohort 1 will include approximately 6 evaluable subjects, which is deemed adequate for the purpose of evaluating safety and PK before Cohort 2 commences.

There are approximately 215 subjects planned for Cohort 2. The primary statistical comparisons will be to assess the ARQ-252 cream 0.3% BID group versus the vehicle BID group, to assess the ARQ-252 cream 0.3% QD group versus the vehicle QD group, and to assess the ARQ-252 cream 0.1% QD group versus the vehicle QD group. A sample size of 55 per active arm and 28 per vehicle arm will provide approximately 85% power at the 2-sided 10% significance level to detect a difference in the rate of subjects attaining an IGA score of clear or almost clear (for each ARQ-252-treated group versus vehicle group within the same daily dosing frequency), assuming an active treatment response rate of 45% and a vehicle response rate of 15%. For testing each active arm of 55 subjects versus the combined vehicle arms of 56 subjects, this sample size provides over 90% power for the comparison of the rate of subjects attaining an IGA score of clear or almost clear. This is based on a 2-group X2 test of equal proportions (without continuity correction).

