### Categorical Data Analysis

The primary efficacy endpoint is the rate of subjects achieving an IGA score of “Clear” or “Almost Clear” at Week 12.

The primary statistical comparisons for Cohort 2 subjects will be as follows:

- ARQ-252 cream 0.3% BID versus vehicle cream (all dose frequencies)
- ARQ-252 cream 0.3% QD versus vehicle cream (all dose frequencies)
- ARQ-252 cream 0.1% QD versus vehicle cream (all dose frequencies)
- ARQ-252 cream (all strengths and dose frequencies) versus vehicle cream (all dose frequencies)
- ARQ-252 cream 0.3% (all dose frequencies) versus vehicle cream (all dose frequencies)

The primary endpoint will be analyzed using a CMH test stratified by pooled study site group and baseline IGA category. Statistical significance will be concluded at the 10% significance level (2-sided) or less, as discussed in [Section 4.1](#). Odds ratios and 90% and 95% CIs for the odds ratios will be provided. Additionally, the 90% and 95% Wilson CIs for proportion of successes in each treatment group will be presented.

For the primary analysis, missing IGA scores will be imputed using multiple imputation as described in [Section 6.1.4](#). These imputations will result in a minimum of 25 to a maximum of 250 complete analysis datasets, depending on the number of imputed monotone datasets required. The CMH analyses will be performed separately for each of the complete analysis data sets, and the results will be combined into one multiple imputation inference (estimated treatment effect and associated CI and *P* value).

The primary efficacy analysis will be based on Cohort 2 subjects in the ITT population.

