## 8.2. Secondary Efficacy Analysis

All secondary efficacy analyses will be performed using the All Treated population for subjects in Cohort 1 and the ITT population for subjects in Cohort 2, unless otherwise specified.

The statistical comparisons for all secondary efficacy endpoints for Cohort 2 subjects will be as follows:

- ARQ-252 cream 0.3% BID versus vehicle cream (all dose frequencies)
- ARQ-252 cream 0.3% QD versus vehicle cream (all dose frequencies)
- ARQ-252 cream 0.1% QD versus vehicle cream (all dose frequencies)
- ARQ-252 cream (all strengths and dose frequencies) versus vehicle cream (all dose frequencies)
- ARQ-252 cream 0.3% (all dose frequencies) versus vehicle cream (all dose frequencies)

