- Percent change from baseline in QOLHEQ score at each visit

The following treatment comparisons were added:

- ARQ-252 cream (all strengths and dose frequencies) versus vehicle cream (all dose frequencies)
- ARQ-252 cream 0.3% (all dose frequencies) versus vehicle cream (all dose frequencies)

For all efficacy treatment comparisons, vehicle cream will be pooled for analysis over both dose frequencies.

Efficacy analysis for Cohort 1 was not specified in the protocol, however, upon request from Sponsor, all efficacy data collected for Cohort 1 (IGA, HECSI, average weekly WI-NRS, average weekly Pain NRS, and % BSA affected by disease) will be summarized.

Subgroup analyses for IGA Success by study site (Week 12 only) and by baseline IGA severity were added.

An analysis of HECSI-75 and total % BSA affected by disease were also requested to be added.

All analyses of time to event (i.e., time to IGA of “clear” or “almost clear”; time to the first achievement of  $\geq 4$ -point reduction from Baseline in WI-NRS pruritus score in subjects with Baseline WI-NRS pruritus score of at least 4; and time to the first achievement of  $\geq 4$ -point reduction from Baseline in Pain NRS score in subjects with Baseline Pain NRS score of at least 4) were removed at the request of the sponsor.

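### The SAP names two different primary comparison sets (frequency-matched vehicle in 3.2, pooled vehicle in 8.1.1), and no planned efficacy output shows vehicle by dosing frequency

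*SAP*

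**What the plan says.** **Matched set.** SAP 3.2 states: "The primary statistical comparisons will be to assess the ARQ-252 cream 0.3% BID group versus the vehicle BID group". It continues in the same way for 0.3% QD and 0.1% QD, each against vehicle QD. Protocol 6.1.1 and 6.2.1 say the same.

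**Pooled set.** SAP 4.1 states: "For the purposes of statistical comparisons, the vehicle BID and vehicle QD groups will be pooled together". The estimand text in SAP 2.2.1.1 says "This estimand shall be estimated using the Cochran-Mantel-Haenszel (CMH) approach and applies to the following treatment comparisons" and then lists five comparisons, all against vehicle combined over both frequencies. SAP 8.1.1 introduces the same five with "The primary statistical comparisons for Cohort 2 subjects will be as follows". SAP 8.2 does likewise for secondary endpoints ("The statistical comparisons for all secondary efficacy endpoints for Cohort 2 subjects will be as follows").

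**Disclosure.** SAP section 10 records: "For all efficacy treatment comparisons, vehicle cream will be pooled for analysis over both dose frequencies". SAP 3.2 also adds a power statement for the pooled control: "For testing each active arm of 55 subjects versus the combined vehicle arms of 56 subjects, this sample size provides over 90% power". Neither place gives a reason for pooling or says that the matched comparisons are no longer primary.

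**Display.** SAP 6.1.9 gives vehicle QD and vehicle BID their own columns in demographic and safety tables, but a single combined vehicle column for efficacy. The Cohort 2 efficacy shells (14.2.1.1.1 to 14.2.3.2) follow that rule. The Cohort 2 sensitivity analyses in SAP 8.1.2 repeat the primary analysis on nonimputed data in the ITT and PP populations. Neither separates vehicle by frequency.

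**The concern.** A reader of SAP 3.2 and a reader of SAP 8.1.1 would name different primary comparisons.

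The second part is substantive. Pooling two vehicle arms as a common control assumes that vehicle response does not depend on how often the cream is applied. The documents assume a single 15% vehicle rate and offer no evidence either way. There are grounds to want a check. Subjects and investigators know whether application is once or twice daily (protocol 4.6), the primary endpoint is investigator-rated, and protocol 2.4.2 says that vehicle may help through moisturising. The design randomised a vehicle arm at each frequency, which would allow the check, but the planned efficacy output merges the two. If the vehicle rates differ, part of an apparent effect of 0.3% BID, 0.3% QD or 0.1% QD would be an effect of application frequency, and the planned tables would not show it.

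**Working it through.** **Inputs.** Arms of 61 (0.3% QD), 61 (0.3% BID), 31 (0.1% QD), 31 (vehicle QD) and 31 (vehicle BID) from protocol 6.1.1 and SAP 3.4. Response 45% active and 15% vehicle, two-sided 10%, chi-square test without continuity correction, evaluable sizes 55, 28 and 56 from SAP 3.2. Vehicle rates that differ by frequency are my assumption.

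**The plan's own power figures.** Power = Φ{[δ − 1.645·√(p̄(1−p̄)(1/n₁+1/n₂))] / √(p₁(1−p₁)/n₁ + p₂(1−p₂)/n₂)}.

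- Pooled, 55 v 56: p̄ = (24.75 + 8.4)/111 = 0.299; (0.300 − 0.143)/0.0823 = 1.91; power 97.2% (exact enumeration 97.4%). This agrees with the stated figure of over 90%.
- Matched, 55 v 28: p̄ = (24.75 + 4.2)/83 = 0.349; (0.300 − 0.182)/0.0952 = 1.24; power 89.3% (exact 90.0%), against the stated 85% or so. The plan's figure is conservative. That is a separate discrepancy, and nothing below depends on it.

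**Bias from pooling.** Let q and b be the true vehicle rates at QD and BID. With 31 in each arm, the pooled rate is (31q + 31b)/62 = (q + b)/2. For a drug with no effect, the expected rate difference is:

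- 0.3% BID: b − (q + b)/2 = (b − q)/2
- 0.3% QD or 0.1% QD: q − (q + b)/2 = −(b − q)/2
- 0.3% at both frequencies: (61q + 61b)/122 − (q + b)/2 = 0
- all active arms: (92q + 61b)/153 − (q + b)/2 = −0.5 points at 12.5%/17.5% and −1.0 point at 10%/20%

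Half the vehicle difference therefore goes into each single-arm comparison, in favour of the arm whose own-frequency vehicle responds better. Either direction is possible.

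**Size for an inert drug.** Exact enumeration of the unstratified test, with the pooled control distributed as the sum of Bin(31, q) and Bin(31, b). The nominal rate is 5% in each direction.

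| Assumed vehicle QD/BID | Odds ratio, 0.3% BID | 0.3% BID falsely better | 0.3% QD falsely worse | 0.1% QD falsely worse | Combined 0.3%, better / worse |
|---|---|---|---|---|---|
| 15% / 15% | 1.00 | 4.9% | 5.0% | 4.6% | 4.6% / 5.1% |
| 12.5% / 17.5% | 1.20 | 10.1% | 10.8% | 8.5% | 4.6% / 5.0% |
| 10% / 20% | 1.42 | 18.0% | 21.3% | 15.1% | 4.5% / 4.9% |

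The odds ratio is odds(b)/odds(0.15); for example (0.20/0.80)/(0.15/0.85) = 1.42. With the rates reversed (20%/10%), an inert 0.3% QD looks better 18.0% of the time and an inert 0.1% QD 16.4%. Tested against its own-frequency vehicle, an inert 0.3% arm stays at 4.6% to 5.1% falsely better in all these scenarios.

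The planned test is a CMH test stratified by site group and baseline IGA, so these are illustrations and not operating characteristics of the trial.

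**What pooling gains.** For 0.1% QD with a 30-point effect, unstratified power moves from matched to pooled as follows: 84.7% to 92.9% at 15%/15%, 87.0% to 89.4% at 12.5%/17.5%, and 89.5% to 84.7% at 10%/20%.

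**Precision of a check.** The 90% half-width for the vehicle difference at 10% v 20% is 1.645·√(0.10·0.90/31 + 0.20·0.80/31) = 0.148, about 15 points. For a 0.3% arm at 45% v 15% the odds ratio is 4.64. Matched (61 v 31), the log standard error is √(1/(61·0.2475) + 1/(31·0.1275)) = 0.565, factor e^(1.645·0.565) = 2.53, giving a 90% CI of about 1.8 to 11.7. Pooled (61 v 62), the log standard error is 0.439, factor 2.06, giving about 2.3 to 9.6.

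**The case against.** The strongest reply is that the operative analysis is not in doubt. SAP 2.2.1.1, 4.1, 8.1.1 and 8.2 and every Cohort 2 efficacy shell use pooled vehicle, and section 10 says so openly. The matched sentence sits in the sample-size section, repeats protocol text, and is followed by the pooled power figure, which suggests the reason for pooling. This largely stands: the first part is a wording correction. A reader might infer that the change was hidden or that the analysis is undefined, and the documents support neither.

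Second, the harm depends on vehicle rates that the documents do not give. At equal rates there is no bias. The moisturising remark does not mention frequency, and subjects in every arm may use their own non-medicated emollients (protocol 4.11.1), which could dilute any frequency effect. This also stands. A reader might infer that the pooled analysis is biased; the documents show only that equality is assumed and that the planned output does not examine it.

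Third, a reader might infer that the trial could not separate drug from frequency at all. It could: the combined 0.3% comparison is balanced on frequency and is already among the five primary comparisons. If BID vehicle does better, the two QD comparisons are conservative. The concern is limited to single-arm claims.

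Fourth, SAP 6.1.4 does not define treatment group in the imputation model, and a reader might infer that imputation blends the vehicle arms. SAP 3.4 speaks of five treatment groups and SAP 4.1 pools only for statistical comparisons, so five arms is the more natural reading.

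What the reply does not answer is that the two vehicle arms could be compared on efficacy only after the fact, from subject listings such as 16.2.6.1.

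**Conclusion.** The inconsistency is certain on the text: SAP 3.2 and 8.1.1 name different primary sets, and section 10 does not settle which has lapsed. It is equally certain that no planned efficacy table or sensitivity analysis shows vehicle by frequency.

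The size of any harm is conditional. It is nil if the two vehicle rates are equal. If they differ by 5 or 10 points around 15%, the single-arm rate differences are off by 2.5 or 5 points, and an inert 0.3% BID arm is falsely favourable about 10% or 18% of the time instead of 5%. Those percentages rest on assumed rates, full planned arm sizes, no missing data and an unstratified test. Keeping pooled vehicle as primary is reasonable. The point is worth fixing because a dose-ranging trial that compares QD with BID should let readers see whether frequency alone matters.

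**What to change.** Before unblinding:

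1. Correct the sentence in SAP 3.2 so that 2.2.1.1, 3.2, 4.1 and 8.1.1 state one primary set in the same words. If pooled vehicle is kept, say in section 10 that the matched comparisons of protocol 6.2.1 are no longer primary, and why.
2. Add to SAP 8.1.2, as pre-specified sensitivity analyses, the three frequency-matched odds ratios with 90% and 95% CIs, using the same CMH test and imputation.
3. Show vehicle QD and vehicle BID columns in the IGA table (14.2.1.1.1) and the HECSI tables (14.2.2.2.1 and 14.2.2.2.3).
4. As a clarification only, confirm that treatment group in the imputation model means the five randomised arms.

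The cost is SAP wording, two columns whose layout already exists in the safety shells, and three odds ratios. Trial conduct does not change. The limitation is precision: with 31 per vehicle arm the check can show direction and rough size but cannot establish equality, so it should not decide whether to pool.

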### 4.2. Interim Analysis and Data Monitoring

No interim efficacy analyses are planned.

## 5. ANALYSIS POPULATIONS

The following analysis populations are planned for this study:

- **Safety Population (SAF):** The Safety population will include all subjects who are enrolled (Cohort 1) or randomized (Cohort 2) and received at least 1 confirmed dose of investigational product (IP). This population will be used for all safety analyses and will be defined separately for each cohort.
- **All Treated Population (ALLTRT):** The All Treated population will include all subjects in the Safety population in Cohort 1. This population will be the primary analysis population for the analysis of Cohort 1 efficacy endpoints.
- **Intent-To-Treat Population (ITT):** The ITT population will include all subjects randomized to Cohort 2. This population will be the primary analysis population for the analysis of Cohort 2 efficacy endpoints.
- **Per Protocol Population (PP):** The PP population will include all subjects in the Safety population in Cohort 2, who were at least 80% compliant with study medication application, and showed no important deviations from the study protocol that would affect the interpretation of efficacy. This population will be used as a sensitivity analysis of Cohort 2 primary and select secondary efficacy endpoints (i.e., IGA, WI-NRS, and HECSI analyses).
- **Pruritus Population (PRU4):** The PRU4 population is a subset of the All Treated population (Cohort 1) and ITT population (Cohort 2) and includes subjects with WI-NRS score  $\geq 4$  at baseline. This population will be used for the analysis of achievement of a 4-point reduction in WI-NRS score as compared to baseline for this subset of subjects.
- **Pain NRS Population (PNRS4):** The PNRS4 population is a subset of the All Treated population (Cohort 1) and ITT population (Cohort 2) and includes subjects with Pain NRS score  $\geq 4$  at baseline. This population will be used for the analysis of achievement of a 4-point reduction in Pain NRS score as compared to baseline for this subset of subjects.
- **Pain NRS Population (PNRS3):** The PNRS3 population is a subset of the All Treated population (Cohort 1) and ITT population (Cohort 2) and includes subjects with Pain NRS score  $\geq 3$  at baseline. This population will be used for the analysis of achievement of a 3-point reduction in Pain NRS score as compared to baseline for this subset of subjects.
- **Pain NRS Population (PNRS2):** The PNRS2 population is a subset of the All Treated population (Cohort 1) and ITT population (Cohort 2) and includes subjects with Pain NRS score  $\geq 2$  at baseline. This population will be used for the analysis of achievement of a 2-point reduction in Pain NRS score as compared to baseline for this subset of subjects.
- **Nail Dystrophy Population (ND):** The ND population is a subset of the ITT population and includes subjects with nail dystrophy at baseline. This population will be used for the analysis of nail dystrophy for this subset of subjects.

- **Pharmacokinetic Population (PK):** The PK population will include all subjects receiving the active drug with sufficient plasma concentrations of ARQ-252 to define a profile, as determined by the pharmacokineticist. This population will be used for analyses of PK parameters.

Assignment of subjects to populations will be confirmed at a blinded data review meeting to be held before the study database is locked.

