Statistical Analysis:	
Descriptive statistics will be presented for the study endpoints. This includes the number and percentage of subjects for binary endpoints/categorical data, and mean, SD, median, minimum, and maximum for continuous data.
 
The primary endpoint in Cohort 2 of 'IGA clear or almost clear at Week 12' will be analyzed using a Cochran-Mantel-Haenszel test stratified by study site and IGA at Baseline. The analysis will be performed on the Intention-to-Treat (ITT) population and missing data will be imputed using multiple imputation.
 
Continuous secondary endpoints measured in Cohort 2 will be analyzed using Analysis of Covariance with treatment and stratification factors as independent variables. The ITT population will be used. Binary secondary endpoints will be analyzed similarly to the primary endpoint.

	
All subjects who are randomized and receive at least one confirmed dose of investigational product will be included in the safety population.
 
Adverse events (AEs) will be summarized within each cohort by preferred term, system organ class, and treatment group (Cohort 2 only) for all treatment-emergent AEs, serious AEs, related AEs, AEs leading to withdrawal from investigational product.
 
Safety laboratory parameters and vital signs will be summarized at each visit using descriptive statistics or frequencies and percentages, as appropriate. Changes from Baseline in laboratory values and vital signs will also be summarized by visit. In addition, changes from Baseline in weight and laboratory values will be summarized using shift tables. These summaries will be tabulated by treatment group for Cohort 2.
 
All subjects who are enrolled and receive at least one application of investigational product and have sufficient pharmacokinetic assessments will be included in the pharmacokinetic population (Cohorts 1 and 2). When possible, the exposure to SHR0302 will be calculated based on plasma concentrations versus time profile data.

--	---

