6.1.2 Subjects to Analyze

Five analysis populations will be defined:

- The Safety population will include all subjects who are enrolled and received at least one confirmed dose of study medication. This population will be used for all safety analyses and will be defined separately for each Cohort.
- The Intent-to-Treat will include all subjects randomized to Cohort 2. This population will be the primary analysis for the analysis of efficacy endpoints.
- The Per-Protocol Population will include all subjects in the safety population, who were at least 80% compliant with study medication application, and showed no important deviations from the study protocol that would affect the interpretation of efficacy. This population will be used as a sensitivity analysis of primary and secondary efficacy endpoints.
- The Pruritis population is a subset of the ITT population and include subjects with WI-NRS score ≥ 4 at Baseline. This population will be used for the analysis of WI-NRS.
- The PK population will include all subjects receiving the active drug with sufficient plasma concentrations of SHR0302 to define a profile, as determined by the pharmacokineticist.

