- h Photography will be performed at selected investigational sites. Photography will be optional. All efforts will be made to de-identify the subjects. Sites participating in optional photography will obtain photos of nail with the worst dystrophy at Baseline/Day 1 and at subsequent visits.
- i A serum pregnancy test will be administered to all females of childbearing potential at Screening. A urine pregnancy test will be administered at Baseline, Weeks 4, 8, 12 and 13. A negative result is required for continued participation in the study, and results must be available prior to dispensing of investigational product.
- j FSH will be performed (if indicated) at Screening to confirm post-menopausal status.
- k PK assessments will be collected from all subjects at Days 1, 29 and 85. The draws will be pre-dose IP application in the clinic.
- l Subjects to apply assigned IP in clinic at these visits. The time of application will be documented.
- m Kits will be dispensed at Baseline, Weeks 2, 4 and 8. Dispensing at Week 12 requires approval from the Medical Monitor. See IP Handling Manual for details.
- n Each IP tube will be weighed prior to dispensing at the Baseline visit and at each follow-up clinic visit according to the Schedule of Visits and Assessments. When IP is applied in the clinic, the IP tube will be weighed before and after IP application. See IP Handling Manual for details.
- o Compliance calculation is described in the IP Handling Manual.
- p Any emergent AEs will be followed in the clinic for up to one month at the Investigator's discretion until resolved or otherwise judged as clinically stable.

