### 13.1.4. Pharmacokinetic Data

#### 13.1.4.1. Pharmacokinetic Data Summary Tables

**Table 11: Pharmacokinetic Data**

Table Number	Population	Table Title / Summary
Table 14.4.1.1	PK	Cohort 1: Summary of Pharmacokinetic Results by Study Visit and Time Point
Table 14.4.1.2	PK	Cohort 2: Summary of Pharmacokinetic Results by Study Visit and Time Point
Table 14.4.2	PK	Cohort 1: Summary of Pharmacokinetic Parameters by Study Visit

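### SAP 5 sends the PK population to a blinded pre-lock meeting, but confirming a Cohort 2 subject as a PK member tells that meeting the subject is on active drug

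*SAP*

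**What the plan says.** SAP 5 defines ten populations, from Safety through to PK, and closes with a single procedural rule: "Assignment of subjects to populations will be confirmed at a blinded data review meeting to be held before the study database is locked". No population is exempted.

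Two of the ten matter here.

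- **PK.** SAP 5 admits "all subjects receiving the active drug with sufficient plasma concentrations of ARQ-252 to define a profile, as determined by the pharmacokineticist". Protocol 6.1.2 sets the same two conditions: "The PK population will include all subjects receiving the active drug with sufficient plasma concentrations of SHR0302 to define a profile". The Statistical Analysis part of the protocol synopsis differs. It asks only for at least one application of investigational product and enough PK assessments, covers both cohorts, and has no active-drug condition.
- **Per-Protocol (PP).** Besides the 80% compliance threshold, members must have "showed no important deviations from the study protocol that would affect the interpretation of efficacy". That is a judgement.

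The PK population is meant to apply to Cohort 2. The Cohort 2 schedule in SAP 3.7 (footnote k) states: "PK assessments will be collected from all subjects at Days 1, 29 and 85". SAP Table 11 plans "Cohort 2: Summary of Pharmacokinetic Results by Study Visit and Time Point" on the PK population. The shell for that table (14.4.1.2) has columns for the three active arms only. The disposition shell (Table 14.1.1) counts PK membership for Cohort 2, and Listing 16.2.3.2 flags it subject by subject.

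SAP 3.6 and protocol 4.6 keep subjects, investigators and site staff blind to product but not to dosing frequency. Neither section restricts access to concentration data or defers PK assignment.

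**The concern.** A population whose entry condition is the treatment received cannot be confirmed by people who must not know the treatment received. If the meeting does as SAP 5 directs, each confirmed Cohort 2 PK member is disclosed as active.

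What is at stake is the credibility of the PP population. Its deviation criterion is settled at the same meeting, while the database is still open. PP is the only restricted-population sensitivity analysis of the Cohort 2 primary endpoint (SAP 8.1.2), and SAP 5 also uses it for WI-NRS and HECSI. If those at the meeting know which subjects are on active drug, the PP exclusions can no longer be described as made blind.

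**Working it through.** The point rests on how the passages fit together, and the plan states no figure to reproduce. The arithmetic below only sizes the disclosure.

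**Logic**

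1. The meeting confirms membership of every listed population before lock, and is blinded (SAP 5).
2. PK membership implies active drug (SAP 5, protocol 6.1.2).
3. Cohort 2 vehicle subjects are sampled too (SAP 3.7), so having samples does not itself reveal the arm. Membership does.
4. Hence P(active, given confirmed PK member) = 1, by definition.

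**Inputs** (SAP 3.4): 0.3% QD 61, 0.3% BID 61, 0.1% QD 31, vehicle QD 31, vehicle BID 31. Active = 61 + 61 + 31 = 153. Vehicle = 31 + 31 = 62. Total = 215, as stated in the plan.

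**What is known before the meeting.** Dosing frequency is open, so the probability of active is:

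- BID: 61/92 = 66%
- QD: (61 + 31)/123 = 92/123 = 75%
- Overall: 153/215 = 71%

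**Members.** All three become 100%. The only active BID arm is 0.3%, so a BID member's arm is known exactly. A QD member is known to be active, but strength stays uncertain: 0.3% with probability 61/92 = 66%.

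**Non-members.** Let q be the share of active subjects who meet the plasma condition. The documents do not give q. I assume the same q in each active arm and show 25% to 100%. Then P(vehicle, given non-member) = n_vehicle / (n_vehicle + n_active × (1 − q)).

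| q | PK members, 153q | BID: 31/(31 + 61(1 − q)) | QD: 31/(31 + 92(1 − q)) | Overall: 62/(62 + 153(1 − q)) |
|---|---|---|---|---|
| Before meeting | – | 31/92 = 34% | 31/123 = 25% | 62/215 = 29% |
| 25% | 38.25 | 40% | 31% | 35% |
| 50% | 76.5 | 50% | 40% | 45% |
| 80% | 122.4 | 72% | 63% | 67% |
| 90% | 137.7 | 84% | 77% | 80% |
| 100% | 153 | 100% | 100% | 100% |

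Disclosure is therefore certain for members at any q above zero. For non-members it is weak at low q and complete only at q = 100%. At q = 0 the Cohort 2 PK population is empty and nothing is disclosed.

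**The case against.** **The meeting is specified as blinded, and the pharmacokineticist makes the determination.** On this view PK was never meant to be shown there. A note to Listing 16.2.3.2 gives reasons for exclusion for Safety, ITT and PP only, which fits a meeting centred on those. This may well be how the meeting would be run. But the text says the meeting confirms assignment and exempts nothing. The pharmacokineticist's role settles who judges adequacy, not who confirms membership.

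**Safeguards may sit in documents not seen here.** The IRT plan and the PK sample manual are separate, and no passage says when Cohort 2 concentrations reach the study team. This stands as a limit: the documents do not show that disclosure would occur. They show only that following the rule as written would cause it.

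**Three pre-dose samples hardly define a profile, so Cohort 2 might have no members.** Read literally, that is arguable. SAP 5 also ties the population to PK parameters, and the only parameter table (14.4.2) is for the open-label Cohort 1. But that reading would empty Table 14.4.1.2, which the SAP plans for Cohort 2 on this population.

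**A reader might infer that any usable Cohort 2 PK criterion breaks the blind.** It does not. The synopsis definition is treatment-neutral and could be confirmed blind from sample collection and timing. The problem belongs to the definition in SAP 5 and protocol 6.1.2.

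**A reader might also infer that all 215 subjects would be unblinded.** That needs q = 100%, which nothing supports. Cohort 2 sampling is pre-dose only, protocol 2.4.1 expects skin absorption to be a small fraction of the applied drug, and the PK listing provides for results below quantification.

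**Conclusion.** The contradiction is real and limited. As written, SAP 5 asks a blinded meeting to confirm a population that, in Cohort 2, only active-treated subjects can enter. Each confirmed member moves from 71% to 100% probability of active, and BID members are identified by exact arm. Non-members move from 29% to roughly 35–100% probability of vehicle, on the assumed 25–100% range for q. These figures use planned arm sizes and a common q.

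The disclosure goes to meeting participants. Sites and subjects, who produce the IGA and diary ratings, are not exposed by it, and QD strength stays hidden.

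It would be wrong to infer that the primary result is compromised. The ITT population is everyone randomised to Cohort 2, so the meeting has no discretion over it. Nor do the documents support predicting a direction or size of bias in PP, since nothing indicates which subjects would be excluded. What is lost is the assurance that the PP deviation judgements were made blind. That is worth protecting when a one-sentence change does it.

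**What to change.** Replace the closing sentence of SAP 5 with wording such as: *Membership of every population other than the Cohort 2 PK population is settled at the blinded data review before lock. Cohort 2 concentration results are not available to that review, and the Cohort 2 PK population is assigned after the database has been locked and unblinded.* Cohort 1 is open label and needs no exemption.

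An alternative with the same effect is to let the meeting confirm only treatment-neutral PK criteria (samples collected, timing valid) and apply the active-drug condition after unblinding.

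Under either option, reconcile the PK definition in the protocol synopsis with protocol 6.1.2 and SAP 5.

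Endpoints, sample size and trial conduct do not change. The cost is that the Cohort 2 PK population is finalised slightly later.
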